6.6 ANALYSIS OF PRIMARY OUTCOME

The primary outcome will be analysed using a Poisson regression model (i.e. generalized linear model with a log link) to assess the differences between the two treatment groups (BUP-XR or MET/BUP-SL). The randomisation stratification variables (centre and current injecting status) will be included in the model as covariates. If a Poisson distribution is not observed then the regression model to be used will be dependent on the distribution of the data and decided following the decision tree in appendix 1, figure 1.

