9.1 By visit

The following standardised instruments will be administered during the study:

Urine drug screen (UDS; detection sensitivity: opiates: 2000ng/ml; cocaine and benzodiazepines: 300 ng/ml; window of detection: 72 hours; UDS procedure conducted each visit). A tamper-proof, instant result, immunoassay device (e.g. E-Z Split Key Cup; www.concateno.com) will screen for recent use of opioids, cocaine and benzodiazepines. The device uses a control line and a temperature sensor (required range: 92°-96 °F) to indicate that a valid test has been done. The UDS product for the study also includes measurement of Bup and Met (providing a proxy indicator of medication adherence) and also (meth)amphetamine and cannabis (for description and exploratory analysis).

* **Structured clinical interview for DSM-5 disorders – research version** (SCID-5-RV [34]). The SCID-5-RV contains a checklist of 11 symptoms (presence or absence) to diagnose the severity of current OUD (mild: 2–3 symptoms; moderate: 4–5; severe: ≥ 6). The American Psychiatric Association's definition for early OUD remission will be applied at 3-month follow-up (i.e. without substance use disorder criteria [except] craving, using the “on maintenance therapy” specifier as appropriate).

Alcohol - Quantity, Frequency and Maximum Consumption (ALC-QFM) This information will be recorded using an adapted version of the **Treatment Outcomes Profile** (TOP [54]). The TOP is the standard national instrument for monitoring the outcomes of public substance use disorder treatment services in England.

Time-Line Follow-Back (TLFB) interview for heroin, cocaine and benzodiazepine recorded for each day whether the participant reports using or not using these drugs. The TLFB, calendar-prompt interview will be adapted from the TOP.

Montreal Cognitive Assessment (MoCA; [35]. The MoCA is a brief screening instrument for mild cognitive impairment and assesses attention, concentration, working memory, visuo-constructional skills, and conceptual thinking. A score of ≥ 26 is considered to reflect normal range functioning. An alternate version of the MoCA will be used at follow-up to decrease the risk of learning effects. The MoCa will be completed on 2 visits: baseline (version 7.1) and study week 12 (version 7.2).

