12.2 Statistical analysis

Assessment of Efficacy

The Statistical Analysis Plan (SAP) - approved by the trial committees - will be published on the Open Science Framework (www.osf.io) and summarised in the published trial protocol paper. After data lock in MACRO for each phase, the statistical analysis will be completed in Stata and R. Pooling data from all clinical treatment sites, a mixed-effects multivariable regression model for the primary analysis, with covariates (sex, age, drug injecting status, centre and baseline score on the outcome measure), and a site-varying random intercept. The medication preference factor will be explored for inclusion through interaction tests because it is expected that many participants have a medication preference given past or current exposure.

A maximum-likelihood multiple imputation approach will be used for the management of missing data with a sensitivity comparison to the complete case dataset. The cumulative distribution function of the primary endpoint will also be plotted for comparison purposes. Analyses of secondary outcomes will proceed using the same stratification and covariates as defined for the primary analysis model with linear (continuous outcomes) or logistic (binary or ordinal outcomes) regression framework. A causal mediation analysis (including craving, MoCa, and WSAS as mediators in separate models) will be implemented using a counterfactual framework to include a treatment/mediator interaction and covariates, based on univariable path screening, and with bias corrected bootstrapped estimates.

The clinical analysis will follow the intention-to-treat principle and include all patients in the group to which they are allocated. Alpha will be set at 5% for the primary and secondary outcomes (with associated 95% confidence intervals). The distributions of scale and count measures may be non-normal (skewed), so test statistics and effect sizes will be computed following appropriate transformation (e.g. natural log to obtain a geometric mean).

Assessment of Cost Effectiveness

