4.2 RANDOMISATION

Online randomisation system will be provided by King's CTU. Randomisation procedure will be on a 1:1 allocation ratio by stratified block with random varying block sizes, stratified for Centre (West Midlands, Manchester, Newcastle and Tayside) and Current (last 28 days) drug injecting status (yes/no). At South London for approximately the first 6 months (subject to change depending on resource and recruitment rates) of recruitment, patients will be randomised to one of four groups on a 4:4:1:1 allocation ratio, with Current (last 28 days) drug injecting status (yes/no). Figure 1 in section 3.1 portrays this.

Justification for these stratification factors is as follows: (a) site is required for the random-effects model; (b) it is expected that there will be relatively poorer outcome among participants who are drug injectors. The randomisation procedure will use stratified random blocks of varying size to ensure even allocation.

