- **Measure 1;** Total retention time - Days enrolled in maintenance medication for opioid use disorder (OUD) from first day following grace period (day 8) to day 168 (across 161 days weeks 2 to 24)
- **Measure 2;** Survival time - Days from randomisation to first discontinuation (i.e. time (days) enrolled in study treatment).
- ***Measure 3;** Time (days) enrolled in study treatment (retention) from week 24 to date last participant randomised plus 9 months.

*Measure 3 Will be analysed as part of the extended phase of the study and detailed in a separate SAP

Objective 4 OUD and CUD remission status

- Assessed by Standard Clinical interview for Dependence - research version (SCID-RV)
 - Remission status (Yes/No) at 12 weeks
 - Remission status (Yes/No) at 24 weeks

Objective 5 Clinician rated impression of patient response to treatment (at 24 weeks)

- **Measure 1;** Clinical Global Impression scale (severity and improvement - CQI-S/CGI-I)
- **Measure 2;** Addiction Dimensions for Assessment and Personalised Treatment (ADAPT)

Objective 6 Patient reported recovery outcomes (at 24 weeks)

Measure 1; Craving response using Craving experience questionnaire (CEQ-F)

Measure 2; Visual analogue craving rating (Need) (VAS-N)

Measure 3; Visual analogue craving rating (Want) (VAS-W)

Measure 4; Social functioning using Work and Social Adjustment Scale (WSAS)

Measure 5; Depression using Quick inventory of Depressive Symptomatology (QIDS-SR)

Measure 6; Improvement and Recovery using Substance Use Recovery Elevator (SURE)

Measure 7; Patient Reported Outcome Status (severity and improvement - PRO-S/PRO-I)

Measure 8; Emotion regulation using Difficulties in Emotion Regulation Scale short form (DERS-SF)

Measure 9; Alcohol quantity, frequency, maximum consumption (ALC-QFM (TOP) - quantity and frequency only - maximum will be reported descriptively).

Objective 7 Mediation analysis

Mediation of craving, work and social adjustment, and cognitive function on outcome.

Mediator measures;

- Visual analogue scale (VAS) for the perceived need and want for non-medical opioids and cocaine (VAS-N and VAS-W)
- Craving Experience questionnaire, frequency version (Heroin) (CEQ-F-H)
- Quick Inventory of Depressive Symptomatology – Self-Report (QIDS-SR)
- Montreal Cognitive Assessment (MoCA)
- Work and Social Adjustment Scale (WSAS)

Moderator measures;

- Sex at birth

- Age
- Current injecting status
- Centre
- Measure/Outcome baseline

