6.7 ANALYSIS OF SECONDARY OUTCOMES

All secondary outcomes are to be analysed as the primary outcome including the randomisation stratification variables (centre and current injecting status) in the models. The model used will be based on the outcome measure (dependent variable) format and the distribution of the data.

- Count variables will be analysed using a Poisson regression model. As with the primary outcome measure the exact model to be used will be based on the distribution of the data following the decision tree in appendix 1, figure 1.
- Continuous measures will be analysed with a GLM to assess the differences between the means of the treatment groups. In addition to the randomisation stratification factors, the baseline measure scores of the associated outcome will be included in the models as covariates to account for the baseline scores.
- Binary variables will be analysed using a (binary) logistic regression model
- Ordinal variables will be analysed using an ordinal logistic regression model

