6.9 SENSITIVITY ANALYSES OR MODEL TESTING

Sensitivity analysis will be conducted on the primary analysis model including the variables that were identified as predictors of missingness as covariates in the model.

Additionally, sensitivity analysis may be required around any assumptions made for the primary analysis (e.g. outliers, data distributions) but will only be conducted if necessary. This will include a best-case worst-case analysis on the self-report missing data on the primary outcome. Best case would assume that patients did not use during any missing time periods and worst case would assume that they did use substances to evaluate any impact the imputed data may have had on the results.

Furthermore, the confidence of the reliability of the self-report will be checked by conducting a best-case worst-case sensitivity analysis on the UDS missing data for the TLFB outcomes.

For those who have a missing UDS, we will assume all missing as negative for one dataset and then for another dataset assume all missing as positive. Utilising this best –worst case scenario will provide a range of values between which the real outcome is likely to lie. The width of this range is likely to be influenced by many factors (including the COVID pandemic and not being able to collect the UDS).

Primary and secondary analysis will be conducted on an ITT basis (including all those randomised to be analysed. Sensitivity analysis may be conducted, if necessary, on protocol deviations or eligibility violations by removing them from the analysis set. This includes protocol deviations (but is not limited to) such as;

- Patients not receiving randomized allocation (per protocol analysis)
- Patients not receiving treatment within 7 days (per protocol analysis)
- Ineligible patients being randomised (mITT analysis)

Sensitivity analysis will be conducted on the patient's months in treatment (for current episode) at baseline by running the model including the variable as a factor.

Additionally, sensitivity analysis of the patient's preference of BUP-SL or MET will be conducted again by running the model including that variable as a factor. This will be conducted given that there is an adequate sample of data per group at each level of the variable (BUP-SL or MET) a sample of 50% – 60% in the MET group will indicate that we will run this sensitivity analysis.

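### SAP 6.6 drops the baseline outcome, sex and age that Protocol 12.2 puts in the primary model, and no sensitivity analysis restores baseline opioid-use days

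*SAP*

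**What the plan says.** Protocol 12.2 describes the primary analysis as a mixed-effects regression "with covariates (sex, age, drug injecting status, centre and baseline score on the outcome measure), and a site-varying random intercept". For the other endpoints it adds: "Analyses of secondary outcomes will proceed using the same stratification and covariates as defined for the primary analysis model".

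SAP 6.6 specifies a Poisson regression comparing the two arms, with Appendix 1 deciding the family if the Poisson does not fit. Its only adjustment is this: "The randomisation stratification variables (centre and current injecting status) will be included in the model as covariates". SAP 6.7 uses the same two factors for secondary outcomes. For continuous measures alone it says that "the baseline measure scores of the associated outcome will be included in the models as covariates".

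Three other places bear on the point:

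- SAP 6.9 has a sensitivity model "including the variables that were identified as predictors of missingness as covariates in the model". The candidates are listed in SAP 4.6.
- SAP 5.2, under the mediation objective, lists sex, age, injecting status, centre and "Measure/Outcome baseline".
- SAP 4.2 justifies stratifying by site because "site is required for the random-effects model", whereas 6.6 enters centre as a covariate.

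**The concern.** Two current documents specify different primary models. The SAP omits the baseline value of the outcome, which is often the most prognostic covariate available, while adjusting for baseline on continuous secondary scales. No reason for the change is visible.

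Validity is not at stake. Under randomisation the stratification-only comparison is sound, its type I error is unaffected, and the sample size does not depend on these covariates. Two things are at stake. One is precision that a scheduled baseline interview might supply at almost no cost. The other is an open choice between two pre-specified primary models in an open-label trial, which should be closed before data lock.

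**Working it through.** **1. The two covariate lists**

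| Term | Protocol 12.2 | SAP 6.6 |
|---|---|---|
| Injecting status | yes | yes |
| Centre | yes | yes |
| Sex | yes | no |
| Age | yes | no |
| Baseline value of outcome | yes | no |
| Site random intercept | yes | no |

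Five covariates are named in the protocol and two in the SAP, so three are missing. Because SAP 6.7 adds baseline only for continuous measures, the cocaine and benzodiazepine day counts lose theirs too.

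**2. Whether a sensitivity analysis restores them**

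The SAP 6.9 models that change covariates add predictors of missingness, months in treatment, medication preference (if numbers allow) or pandemic enrolment period (if judged necessary). The missingness candidates in SAP 4.6 include sex and age, so those two return only if they predict missingness. The baseline scores on that list are QIDS-SR, WSAS, PRO-S, ALC-QFM and ADAPT. TLFB opioid days are not named. The other SAP 6.9 analyses change the data or the analysis set, not the covariates. The protocol's primary model is therefore not specified anywhere in the SAP.

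**3. Whether the variable is collected**

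TLFB is marked at baseline in Protocol 9.2 and in SAP 5.1, Table 1. Its baseline look-back window is not stated. Protocol 9.1 describes it as an "interview for heroin, cocaine and benzodiazepine recorded for each day whether the participant reports using or not using these drugs", while the endpoint covers all non-medical opioids.

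**4. Size of the precision loss, by formula**

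The plan gives no figure for this and no baseline-outcome correlation. Let r be the correlation that remains after centre and injecting status (assumed). The standard error with baseline, relative to without, is about √(1 − r²):

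| r | √(1 − r²) | SE smaller by about |
|---|---|---|
| 0 | 1.000 | 0% |
| 0.2 | √0.96 = 0.980 | 2% |
| 0.3 | √0.91 = 0.954 | 5% |
| 0.4 | √0.84 = 0.917 | 8% |
| 0.5 | √0.75 = 0.866 | 13% |
| 0.6 | √0.64 = 0.800 | 20% |

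**5. Check in a log-link count model**

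The formula is for a linear model. In a Poisson model the gain arises only through overdispersion, when baseline absorbs between-patient variation beyond Poisson, so this was simulated:

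- 304 × 0.85 ≈ 258 patients (target and attrition from SAP 4.1), 161 days, about 60% of days abstinent.
- Logit-normal patient effects with SD 1, 2 or 3, giving Pearson dispersion of about 11, 26 and 35 (assumed).
- Poisson log-link model with Pearson-scaled standard errors, adjusted for five sites and injecting status, with and without a 28-day baseline count (assumed window).
- 400 replicates per setting.

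Ratios below are with baseline divided by without, for SD 1, 2, 3:

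| Residual r | Empirical SE ratio | Reported SE ratio |
|---|---|---|
| 0 | 1.000 to 1.004 | 1.002 to 1.003 |
| about 0.22 | 0.986, 0.971, 0.980 | 0.983, 0.987, 0.992 |
| about 0.45 | 0.891, 0.892, 0.918 | 0.917, 0.934, 0.955 |
| about 0.64 | 0.792, 0.775, 0.788 | 0.820, 0.844, 0.881 |

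The empirical SE is thus 1–3%, 8–11% and 21–23% smaller in the last three rows, and the reported SE 1–2%, 5–8% and 12–18% smaller. A second simulation (300 replicates per setting) at residual r of about 0.27, 0.49 and 0.68 gave empirical ratios of 0.94–0.99, 0.86–0.90 and 0.74–0.76, the same pattern.

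**The case against.** The strongest reply is that the SAP is where detail is meant to be settled. Protocol 5.3 defers to it, and adjusting only for stratification factors is a defensible pre-specified choice. The gain depends on an r that neither document gives, and at r of about 0.2 it is only some 2%. Nothing quantifies a gain from sex or age. This all stands, and it is why the sizes are illustrative and no power figure is claimed. It does not remove the conflict: dropping three named covariates changes the protocol's model rather than detailing it.

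The baseline version of the outcome is also undefined. Its window is not given, the interview is described in terms of heroin, and the schedule tables as extracted show urine screening only after baseline. What is available may be a self-report proxy. This stands as a condition on the fix: a proxy can still be prognostic, and adjusting for an uninformative one costs very little.

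Three smaller points are fair. Part of the SAP's version history was not in the text reviewed, so a recorded reason cannot be ruled out. The baseline entry in the mediation list may mean the mediator's baseline. The sentence in SAP 4.2 about random effects repeats the rationale in Protocol 8.4 and does not itself specify a model. None of these supplies the missing covariates.

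**Conclusion.** The concern holds. SAP 6.6 omits three of the five covariates in Protocol 12.2, and no SAP sensitivity model names baseline opioid-use days. This should be fixed, but it does not threaten validity: there is no bias, no effect on type I error and no effect on the target of 304.

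By the formula, the standard error given up is about 2% at r = 0.2, 8% at 0.4 and 20% at 0.6. The simulations give similar empirical gains and somewhat smaller reported ones. If baseline carries no information, adding it raises the reported standard error by about 0.3%. These sizes rest on an assumed residual correlation, assumed overdispersion and an assumed 28-day baseline window. Sex and age are a matter of consistency between the documents; no precision gain is claimed for them.

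**What to change.** Before data lock:

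- **SAP 6.6.** State that the primary model, whichever family Appendix 1 selects, contains arm, centre, injecting status, age, sex and baseline TLFB days abstinent. If that family has two parts, say which part carries the covariates.
- **Baseline definition.** Give the look-back window (for example 28 days, as already used for injecting status, if the baseline interview covers it). Match the substance to the endpoint as far as the baseline TLFB allows, and use self-report if there is no baseline urine screen.
- **Missing baseline values.** Fill with the overall mean across both arms, not by arm.
- **SAP 6.7.** Add the matching baseline counts for the cocaine and benzodiazepine day outcomes.
- **Both documents.** State once whether centre is fixed or random, and align Protocol 12.2 with SAP 4.2 and 6.6.
- **SAP 6.9.** Keep the stratification-only model as a sensitivity analysis.

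If the sponsor prefers the present SAP model, it should record why and amend Protocol 12.2 to match.

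The cost is a few SAP sentences, one protocol edit and three extra parameters (baseline days, age, sex). No new visit is needed because the TLFB is already scheduled at baseline, but its look-back window must be confirmed.

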6.7 ANALYSIS OF SECONDARY OUTCOMES

All secondary outcomes are to be analysed as the primary outcome including the randomisation stratification variables (centre and current injecting status) in the models. The model used will be based on the outcome measure (dependent variable) format and the distribution of the data.

- Count variables will be analysed using a Poisson regression model. As with the primary outcome measure the exact model to be used will be based on the distribution of the data following the decision tree in appendix 1, figure 1.
- Continuous measures will be analysed with a GLM to assess the differences between the means of the treatment groups. In addition to the randomisation stratification factors, the baseline measure scores of the associated outcome will be included in the models as covariates to account for the baseline scores.
- Binary variables will be analysed using a (binary) logistic regression model
- Ordinal variables will be analysed using an ordinal logistic regression model

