10.2 Secondary Efficacy Parameters

There will be 19 secondary within-study efficacy parameters:

- (1) Clinical superiority of XR-Bup plus PSI versus Bup/Met plus PSI using the primary outcome measure;
- (2) Safety measured by all adverse event reporting;

- (3) Time (days) enrolled in study treatment (retention) to week 24;
- (4) OUD and CUD remission status (severity) measured by SCID-5-RV for DSM5;
- (5) Clinician rating of severity, complexity and recovery strengths (ADAPT);
- (6) Clinician rating of global impression (CGI-I anchored on baseline severity [CGI-S]);
- (7) Count of days abstinent from cocaine and illicit/non-medical benzodiazepines during weeks 2 to 24 (range: 0-161 days); combining self-report information from Time-Line Follow-Back interview adapted from the Treatment Outcomes Profile and incorporating data from 12 scheduled urine drug screens;
- (8) Craving for opioids and cocaine (CEQ-F[H] and CEQ-F[C]);
- (9) VAS-N and VAS-W craving need for heroin and cocaine;
- (10) Difficulties in Emotion Regulation – Short Form (DERS-SF);
- (11) QIDS-SR (depression rating);
- (12) WSAS (work and social adjustment);
- (13) Subjective recovery and improvement (SURE);
- (14) Subjective rating of OUD improvement (PRO-I; on baseline severity [PRO-S]);
- (15) Cognitive impairment (MoCA);
- (16) Alcohol: typical quantity and frequency (ALC-QFM)
- (17) Time (days) enrolled in study treatment (retention) from week 24 to date last participant randomised plus 9 months;
- (18) Semi structured, topic guided interviews after week 24 (XR-Bup, XR-Bup +PSI & Bup/Met +PSI treatment arms) and after 12 months of enrolment within the trial (XR-Bup treatment arm only);
- (19) Among participants enrolled in longer term XR-Bup treatment: OUD and CUD remission status (SCID-5-RV); heroin, cocaine and illicit/non-medical benzodiazepine use in past 90 days (TLFB; UDS); somatic symptoms (PHQ-15), emotion regulation (DERS-SF), depression and anxiety symptoms (PHQ-4) and quality of life (OSTQOL).

Analysis of other research measures will be specified in the statistical analysis plan.

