5.1 TIME POINTS OF OUTCOMES MEASURES

Table 2 indicates the data and study measures to be collected during the trial and at which time points across the study they are collected.

Table 1: List of outcome measures to be collected and time point of collection

Measure	Baseline	Randomisation	Ongoing	Week 1	Week 2	Week 4	Week 6	Week 8	Week 10	Week 12	Week 14	Week 16	Week 18	Week 20	Week 22	Week 24	Withdrawal	Week 24 onwards	Ext. Phase Interview ++
Consent §	X																	X	X
Screening	X																		
UDS				X	X	X	X	X	X	X	X	X	X	X	X				
LFT *	X					X				X						X		X	
BUP-XR**				X		X		X		X		X		X				X	
BUP-SL/MET **		X																	
ALC-QFM (TOP)***	X																X		
SCID-5-RV	X									X						X			X
ADAPT	X					X				X						X			
CGI-S	X																		
CGI-I						X				X						X			
CEQ-F – H***	X					X		X		X		X		X		X	X		
CEQ-F – C***	X					X		X		X		X		X		X	X		
VAS-N (H/C)***	X					X		X		X		X		X		X	X		
VAS-W (H/C)***	X					X		X		X		X		X		X	X		
DERS-SF	X					X				X						X			X
WSAS	X					X				X						X			
EQ-5D-5L	X									X						X			
AD-SUS	X									X						X			
KCF***							X			X						X			
QIDS-SR	X					X				X						X			
SURE							X			X						X			
PRO-S	X																		
PRO-I								X			X					X			
MoCA***	X									X									
OSTQOL																		X	
PHQ-4																		X	
PHQ-15																		X	
Exit Interview+																	X		
BUP-SL/MET + PSI Interview++																X			
TLFB	X	X																	X
Con Meds****		X				X				X						X		X	
Adverse Events Log		X																X	
Research Payments *****	X		X	X	X	X	X	X	X	X	X	X	X	X	X			X	
	20		10	10	10	5	10	1	10	5	10	10	10	5	10			20	

§ screening to include pregnancy test, demographics and medical history. Participants receiving XR- BUP-SL reconsented once at week 24 to continue receiving monthly injections;

* LFT for all participants at screening; during treatment for BUP-XR participants only under protocol;

** refer to section 6 of the protocol for guidelines;

*** used for mediation model;

**** ConMeds to be recorded continuously and reviewed at week 4, 12 and 24;

***** research payments are time offset to attend the clinic to complete research measures and cover travel (either a £20, £10, or £5 value, as detailed per visit applicable; loaded onto a prepaid card).

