APPENDIX 2 – OBJECTIVES AND ASSOCIATED OUTCOME MEASURES AND CHARACTERISTICS

Objective	Outcome Measure	Time Period	End point	Variable Type	Analysis Model	Scoring
One - effectiveness of BUP-XR and MET/BUP-SL	Primary outcome					
	Number of days abstinent from heroin	Days 8 – 168	24 weeks	Count	Poisson Regression	Count of days abstinent
	Secondary outcomes					
	Number of days abstinent from cocaine	Days 8 – 168	24 weeks	Count	Poisson Regression	Count of days abstinent
	Number of days abstinent from Benzodiazepines	Days 8 – 168	24 weeks	Count	Poisson Regression	Count of days abstinent
	Longest time in days continuously abstinent from heroin	Days 8 – 168	24 weeks	Count	Poisson Regression	Max Count of days consecutively abstinent
	Longest time in days continuously abstinent from cocaine	Days 8 – 168	24 weeks	Count	Poisson Regression	Max Count of days consecutively abstinent
	Longest time in days continuously abstinent from Benzodiazepines	Days 8 – 168	24 weeks	Count	Poisson Regression	Max Count of days consecutively abstinent
Two – Safety profile	Number of safety events	Study enrolment to 24 weeks	24 weeks	Count	Descriptive	n/a
Three – Treatment retention	Total retention time	Days 8 – 168	24 weeks	Count	Poisson Regression	Count of Days enrolled in maintenance medication for OUD
	Survival time to study withdrawal	Randomisation date to first discontinuation	24 weeks	Time to event	Cox regression	Time to first discontinuation
Four – OUD and CUD remission status	SCID-RV interview	Baseline to week 24	12 weeks & 24 weeks	binary	(Binary) logistic regression	Remission status (Yes/No) indicated by SCID-RV (see appendix 3 for SCID scoring)

Objective	Outcome Measure	Time Period	End point	Variable Type	Analysis Model	Scoring
Five – Clinician rated impression of patient response to treatment	Clinical Global Impression scale (severity and improvement - CQI-S/CGI-I)	Baseline to week 24	24 weeks	Ordinal	Ordinal logistic Regression	See Appendix 3
	Addiction Dimensions for Assessment and Personalised Treatment (ADAPT)	Baseline to week 24	24 weeks	Continuous	GLM	See Appendix 3
Six – Patient reported recovery outcomes	Craving response using Craving experience questionnaire (CEQ-F)	Baseline to week 24	24 weeks	Continuous	GLM	See Appendix 3
	Visual analogue craving rating (Need) (VAS-N)	Baseline to week 24	24 weeks	Continuous	GLM	See Appendix 3
	Visual analogue craving rating (Want) (VAS-W)	Baseline to week 24	24 weeks	Continuous	GLM	See Appendix 3

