	Social functioning using Work and Social Adjustment Scale (WASAS)	Baseline to week 24	24 weeks	Continuous	GLM	See Appendix 3
	Depression using Quick inventory of Depressive Symptomatology (QIDS-SR)	Baseline to week 24	24 weeks	Continuous	GLM	See Appendix 3
	Improvement and Recovery using Substance Use Recovery Elevator (SURE)	Week 4 to week 24	24 weeks	Continuous	GLM	See Appendix 3
	Patient Reported Outcome Status (severity and improvement - PRO-S/PRO-I)	Baseline to week 24	24 weeks	Ordinal	Ordinal logistic Regression	See Appendix 3
	Emotion regulation using the Difficulties in Emotion Regulation Scale- short form (DERS-SF)	Baseline to week 24	24 weeks	Continuous	GLM	See Appendix 3
	Alcohol quantity, maximum consumption (ALC-QF (TOP))	Baseline to week 24	24 weeks	Continuous	GLM	See Appendix 3

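### The SAP's ordinal models for CGI-I and PRO-I omit the baseline CGI-S and PRO-S scores that Protocol 10.2 names as their anchors, and its baseline-covariate rule has no valid input for SURE

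*SAP*

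**What the plan says.** SAP 6.7 gives every secondary model the two stratification variables, centre and current injecting status. For continuous measures it adds that "the baseline measure scores of the associated outcome will be included in the models as covariates to account for the baseline scores". The ordinal bullet reads only "Ordinal variables will be analysed using an ordinal logistic regression model".

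**CGI and PRO.** Protocol 10.2 lists "Clinician rating of global impression (CGI-I anchored on baseline severity [CGI-S" and "Subjective rating of OUD improvement (PRO-I; on baseline severity [PRO-S" as secondary parameters, with the severity item in brackets as the reference point. SAP 5.2 puts severity and improvement together under objectives that are headed as week-24 assessments. Appendix 2 does the same: the row "Clinical Global Impression scale (severity and improvement - CQI-S/CGI-I" is ordinal with a 24-week endpoint, and the PRO row follows the same pattern. The schedule in SAP 5.1 ("Table 1: List of outcome measures to be collected and time point of collection") and the one in Protocol 9.2 mark CGI-S and PRO-S at baseline only, and CGI-I and PRO-I at follow-up only. Protocol 9.1, however, describes PRO-S as rated at baseline and again later.

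**SURE.** Appendix 2 lists "Improvement and Recovery using Substance Use Recovery Elevator (SURE" as a continuous outcome analysed by GLM at 24 weeks, with the time period "Week 4 to week 24". The other continuous rows in that appendix start at baseline.

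**Covariates in the protocol.** Protocol 12.2 carries the primary model's covariates into the secondary analyses, and these include a baseline score on the outcome measure.

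**The concern.** The baseline rule depends on the type of variable and was not checked against what the schedule supplies. It therefore misses in two places.

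For CGI-I and PRO-I, a pre-randomisation severity rating by the same rater (clinician or patient) exists, and the protocol pairs it with the outcome. Because the outcome is ordinal, the rule does not reach it. At stake are some precision and agreement with the protocol's definition of these two outcomes.

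For SURE the rule does apply, but there is no pre-randomisation score to enter. The analyst has to choose: drop the term, substitute another baseline measure, or treat the first available SURE score as if it were baseline. The last choice would adjust for something that treatment may already have changed, because Protocol 8.3 expects the first XR-Bup injection within 7 days of randomisation. The choice should be fixed before the data are seen.

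**Working it through.** The plan states no figure on this point, so the check is a comparison of the documents followed by one piece of algebra.

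**Step 1. What each model needs and what is collected.**

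| Measure | Marked at baseline (Protocol 9.2, SAP 5.1) | Type in Appendix 2 | Baseline term under SAP 6.7 | Protocol 10.2 |
|---|---|---|---|---|
| CGI-I | No, but CGI-S is | Ordinal | None named | Anchored on CGI-S |
| PRO-I | No, but PRO-S is | Ordinal | None named | Set on PRO-S |
| SURE | No | Continuous | Required | No anchor named |
| ADAPT, CEQ-F, VAS-N, VAS-W, WSAS, QIDS-SR, DERS-SF, alcohol | Yes | Continuous | Required and available | No anchor named |

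The column positions of later visits are unreliable in the text version of the two schedules, so the week-4 start for SURE rests on Appendix 2. Neither schedule shows a baseline mark for SURE.

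**Step 2. CGI-I and PRO-I.** The input that Protocol 10.2 points to is collected, but the SAP's outcome models do not use it. The gain from adding it depends on how strongly baseline severity predicts the week-24 rating. The documents give no such correlation, so the gain cannot be stated.

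**Step 3. SURE.** Let D24 be the true week-24 difference between arms, D4 the difference already present at the first SURE visit, and b the within-arm slope of the week-24 score on the earlier score. Adjusting for the earlier score gives an expected estimate of

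D24 − b × D4.

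If D4 = 0 there is no bias, and the covariate helps precision. If D4 has the same sign as D24 and b is positive, the estimate is pulled toward zero by b × D4.

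The identity was checked with assumed values: D24 = 0.30 SD, b = 0.5, and 129 per arm (304 × 0.85 / 2 = 129.2). For D4 = 0 the formula gives 0.30, and 2,000 simulated trials averaged 0.30. For D4 = 0.15 SD it gives 0.30 − 0.5 × 0.15 = 0.225, and the simulations averaged 0.224. This confirms only the direction and the condition for bias. None of these inputs comes from the documents, and the SAP does not plan this analysis, so the figures are not an expected loss.

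**Step 4. PRO-S timing.** Protocol 9.1 implies a follow-up PRO-S, whereas both schedules show baseline only. The documents do not settle which is intended.

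**The case against.** The strongest reply on CGI-I and PRO-I is that anchoring can lie in the rating itself. These are change ratings by construction: SAP Appendix 3 describes the CGI as covering change since treatment began, and PRO-I runs from improved to worse. Protocol 10.2 does not say that CGI-S or PRO-S must be a regression covariate. The covariate in Protocol 12.2 is the baseline score on the same measure, which CGI-I and PRO-I do not have. All of that stands. Leaving the severity scores out does not bias a randomised comparison, and adding them is an improvement rather than the repair of an invalid model. It is still worth making, because the scores are already collected and the SAP adjusts its continuous outcomes in the same way.

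Four stronger readings are tempting, and the documents do not support them:

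- A reader might infer that the week-4 SURE score will serve as the baseline, so that the SURE effect will be attenuated. The SAP says no such thing. An equally natural reading is that the term drops out and the stratification factors remain.
- A reader might infer that the SAP plans to analyse severity at week 24. The combined label, with a period running from baseline to week 24, can equally mean baseline severity plus week-24 improvement.
- A reader might infer that no week-24 severity score can exist. The schedules support this for CGI-S, but for PRO-S, Protocol 9.1 points the other way.
- A reader might infer that CGI-S and PRO-S are not used at all. CGI-S is a subgroup factor for the primary outcome (SAP 6.8). PRO-S is a candidate predictor of missingness (SAP 4.6) and, if identified as one, would enter imputation models and a sensitivity model of the primary outcome (SAP 6.9).

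**Conclusion.** The point holds in a limited form. The SAP's CGI-I and PRO-I models omit baseline severity scores that are available and that Protocol 10.2 names. Adding them costs nothing in data, and the size of the gain cannot be worked out from the documents. The SAP 6.7 baseline rule cannot be carried out for SURE, and the SAP neither makes an exception nor names a substitute. Bias would arise only if a post-randomisation SURE score were used as a covariate and a treatment effect had appeared by that visit. The SAP does not state the first condition and the second is unknown, so no percentage loss is claimed. The severity-and-improvement labels and the PRO-S timing are matters for clarification. SAP 4.3 treats all secondary outcomes as exploratory, and the primary result is untouched.

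**What to change.** - **SAP 6.7, ordinal outcomes:** add baseline CGI-S as a covariate in the CGI-I model and baseline PRO-S in the PRO-I model, and say whether each enters as a linear score or as categories.
- **SAP 5.2 and Appendix 2:** name CGI-I and PRO-I as the week-24 outcomes and show CGI-S and PRO-S as their baseline covariates.
- **SAP 6.7 and the SURE row of Appendix 2:** state that SURE has no pre-randomisation score; that its week-24 model uses the stratification factors, optionally with pre-randomisation scores already collected (for example PRO-S, WSAS or the ADAPT recovery-strengths subscale, named in advance); and that no post-randomisation SURE score is a covariate.
- **Protocol 9.1 and the two schedules:** reconcile the timing of PRO-S.

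The cost is a wording amendment, with no new data, visits or sample. The CGI-I and PRO-I odds ratios would become conditional on baseline severity as well as on centre and injecting status, which the report should state. SURE loses nothing, since it never had a valid baseline score on its own scale.
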